Patients will be screened by a member of the research team. Patients will be adults (men and women) who have been identified by a provider as having pre-diabetes (A1c 5.7-6.4) or diabetes (A1c 6.5 or above) and: 1.) Enter one of the two diabetes programs during the study; 2.) Self-identify as “Latino;” 3.) Can identify a social support or key member of their social network who will agree to participate with them; 4.) Are not pregnant (participants who become pregnant during the study will be excluded); and 5.) Have household income 250% of the FPL or below. Participants who become pregnant during the study will be excluded. Additionally, we have discovered that there is a difference between the A1c test that CTSC runs and the test run at Quest or TriCore. The test CTSC uses is reliably .2 lower and this is cited in the literature. Therefore, it is appropriate for us to enroll individuals who have a test at another lab that shows them to be pre-diabetic (A1c 5.7-6.4) even if our baseline lab comes back lower (5.5-6.2). However, any individual whose blood gathered by our data collectors at baseline returns with an A1c below 5.5 will be disenrolled.

Social supports will be adult individuals who are identified by the patient participants and who agree to participate.

Advisory Board Members will be seven members of our Project Patient Advisory Board.

PROTOCOL TITLE: Comparing Program Options for Latinos with Diabetes

3.3 Indicate specifically whether you will include or exclude each of the following special populations: (You may not include members of the above populations as subjects in your research unless you indicate this in your inclusion criteria.)

1. *Adults unable to consent*
2. *Individuals who are not yet adults (infants, children, teenagers)*
3. *Pregnant women*
4. *Prisoners*

We will not recruit:

- Adults unable to consent
- Individuals who are not yet adults (infants, children, teenagers)
- Prisoners
- Pregnant women.

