At enrollment, we will screen to specifically exclude participants who are pregnant. There is no risk to a pregnant woman or a fetus entailed in participation in this study because the study only involves data collection from individuals who have been instructed to participate in a diabetes self-management program by their provider. However, we will exclude pregnant individuals because we recognize that pregnancy could impact outcomes in a way that will influence our scientific analysis of diabetes self-management. At each data collection point, we will ask female participants if they are pregnant. If we discover that a participant has become pregnant during the course of the study, they will be given an end-of-study visit to end their participation and their data will be excluded. Co-I [name] will give them a referral to the UNM specialty prenatal clinic for high-risk pregnancies. It will be made clear to them that ending their participation in our study does not affect their ability to continue participating in the diabetes program that they attend.

This study involves regular screening for A1c levels. For A1c (>10), we will notify the participant's PCP. If we see a lab value that could indicate an emergency (Glucose > 400 mg/dl, < 60 mg/dl), we will contact the participant to make sure they are aware of their A1c status and that they are receiving appropriate care. If the participant would like more information about what to do, Co-Investigator [name] will advise them. For women with an elevated A1c, when we contact them to tell them about their elevated test results we will inquire whether or not they are or think they might have become pregnant since entering the study.

PROTOCOL TITLE: Comparing Program Options for Latinos with Diabetes

If so, Co-Investigator [name] will provide them with a referral to UNM's High Risk Obstetrics Clinic.

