A1c: The PDCSs will be trained in phlebotomy. The PDCS will draw blood samples at the same time they administer the survey. The UNM Clinical and Translational Science Center (CTSC) Clinical Research Laboratory will provide the collection kits for specimen collection. Blood will be drawn, labeled and stored using standard phlebotomy protocols, and the *Patient Engagement Coordinator* will deliver specimens to the CTSC lab where they will be tested on whole blood following the lab's "*Hemoglobin A1c*" procedure using the DCA Vantage 2000 analyzer⁹¹. After testing, specimens will be disposed of according to CTSC lab protocol. For A1c (>10), we will notify the participant's PCP. If we see a lab value that could indicate an emergency (Glucose > 400 mg/dl, < 60 mg/dl), we will contact the participant to make sure they are aware of their A1c status and that they are receiving appropriate care. For women with an elevated A1c, when we contact them to tell them about their elevated test results we will inquire again whether or not they are or think they might be pregnant. If so, Co-Investigator [name] will provide them with a referral to UNM's High Risk Obstetrics Clinic. Additionally, we have discovered that there is a difference between the A1c test that CTSC runs and the test run at Quest or TriCore. The test CTSC uses is reliably .2 lower and this is cited in the literature. Therefore, it is appropriate for us to enroll individuals who have a test at another lab that shows them to be pre-diabetic (A1c 5.7-6.4) even if our baseline lab comes back lower (5.5-6.2). However, any individual whose blood gathered by our data collectors at baseline returns with an A1c below 5.5 will be disenrolled.

Body Mass Index (BMI): The PDCS will document patient participant height and weight and calculate his or her BMI. Height and weight measurements will be taken using a standardized protocol. Height measurements will be collected using SHORR boards against

PROTOCOL TITLE: Comparing Program Options for Latinos with Diabetes

flat walls on level, firm (not carpeted) flooring. Weight measurements will be collected using calibrated, research-grade SECO scales. Two measurements will be taken for height and two for weight for each participant at each data collection point. An average of the two measures of height and an average of the two measures of weight will be used in the BMI calculation.

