13.0 Withdrawal of Subjects*

13.1 Describe anticipated circumstances under which subjects will be withdrawn from the research without their consent.

We do not anticipate that individuals will be withdrawn without their consent.

13.2 Describe any procedures for orderly termination.

PROTOCOL TITLE: Comparing Program Options for Latinos with Diabetes

Participation for women who become pregnant during the study will be ended. They will be given an end-of-study visit where we will inform them that we are unable to continue their participation in the study and we will thank them for their participation. They will be told that their participation in the diabetes program they attend will not be affected by the fact that they have ended participation in the study.

13.3 Describe procedures that will be followed when subjects withdraw from the research, including partial withdrawal from procedures with continued data collection.

Participation for women who become pregnant during the study will be ended. They will be given an end-of-study visit where we will inform them that we are unable to continue their participation in the study and we will thank them for their participation. They will be told that their participation in the diabetes program they attend will not be affected by the fact that they have ended participation in the study.

Our Data Manager will create a separate project on REDCap to track individuals who have withdrawn themselves, been withdrawn due to pregnancy, or who have discontinued as a result of attrition.

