Statistical methods using validated methods to handle missing data (MD-2, MD-3). As described above, all attempts to minimize missing data will be made. Despite these attempts, we realistically expect there to be some degree of missingness. Of particular interest is whether participants are missing any outcome data. We will determine whether it is missing completely at random (MCAR), missing at random (MAR), or missing not at random (MNAR). MCAR is defined as missingness that is independent of the observed and unobserved data (example: A1c measurement not obtained due to random machine failure); MAR is defined as missingness dependent only on an observed variable within the data (example: participant accidentally skips one question on the PAM-13); and MNAR is a systematic pattern to or a reason for the missingness (example: many participants exclude answering a question on the DKQ for a specific reason, either accidentally or intentionally). For MNAR, we will perform sensitivity analyses such as conducting the primary and secondary analyses on the intention-to-treat and per-protocol populations and compare the results. Under the assumption that most missing data is MAR or MCAR, we may use multiple imputation¹²⁶⁻¹²⁹ to create imputed data sets containing estimates from a random sample of missing values for each observation based on other non-missing covariates for each subject. Each imputed data set is then analyzed as described in the statistical analysis plans for the outcome measures, and the results from each analyzed data set are combined for statistical inference. Multiple

imputation will be performed using PROC MI and PROC MIANALYZE in SAS 9.4 or in Stata 13.1 or higher.

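### The pregnancy exclusion in 3.3 is not limited to visits after the pregnancy began, so read literally it removes valid earlier data, including completed 6-month primary outcomes

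*Combined protocol and SAP*

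**What the plan says.** Section 3.3 screens out pregnancy at enrollment and asks again during follow-up: "At each data collection point, we will ask female participants if they are pregnant". If a pregnancy is discovered, "they will be given an end-of-study visit to end their participation and their data will be excluded". The only reason given is that "pregnancy could impact outcomes in a way that will influence our scientific analysis of diabetes self-management"; the same paragraph says participation carries no risk to the woman or fetus.

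Section 3.2, which defines the final study sample, states that "participants who become pregnant during the study will be excluded", and says so twice.

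Sections 13.2 and 13.3 each state: "Participation for women who become pregnant during the study will be ended". 13.3 adds a tracking list for those who withdrew themselves, have "been withdrawn due to pregnancy, or who have discontinued as a result of attrition". Neither says what happens to data already collected.

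The A1c procedures add a second route to detection. For women with an elevated result, 9.2 says "we will inquire again whether or not they are or think they might be pregnant". Section 3.3 has a similar follow-up, and 9.3 adds that women found pregnant this way leave the study.

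On missing data, 13.3 offers as a sensitivity analysis "conducting the primary and secondary analyses on the intention-to-treat and per-protocol populations". It defines neither population, and multiple imputation is optional.

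**The concern.** The stated reason covers measurements taken during pregnancy. It does not cover measurements completed before pregnancy began, yet the exclusion in 3.3 has no such limit. Ending participation already stops later data, so the added clause about data most naturally refers to what has already been collected.

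Two things are at stake. First, valid outcomes are lost. The primary outcomes are changes from baseline to 6 months (11.2), while follow-up runs to 12 months (7.1). A pregnancy that begins after month 6 leaves the primary outcome complete and unaffected, and the rule removes it.

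Second, membership of the analysis set depends on something that happens after program entry. The comparison is not randomized and relies on propensity scores built from pre-treatment characteristics (11.1), which cannot correct for removal triggered later. Because women with an elevated A1c are asked about pregnancy again, removal is also partly linked to a secondary outcome.

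**Working it through.** **Reading the sections together**

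| Section | Participation | Data already collected |
|---|---|---|
| 3.2 | Later pregnancy is an exclusion from the final sample | Not addressed separately |
| 3.3 | Ended | Excluded, with no time limit |
| 9.3 | Excluded from the study | Not addressed |
| 13.2–13.3 | Ended and tracked | Silent |

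No section retains visits completed before the pregnancy.

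**Reproducing the plan's figures (11.2)**

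Completers: 120 × (1 − 0.20) = 96 per site, as stated.

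Power is for a two-sided, two-sample t test with n per site, noncentrality Δ / (SD × √(2/n)) and 2n − 2 degrees of freedom. At n = 96:
- DKQ, Δ = 2.2, SD = 3.8, alpha 0.025: 95.9% (stated 96%).
- PAM-13, Δ = 12.7, SD = 24.8, alpha 0.025: 90.0% (stated 85%). At alpha 0.0125, the other level given in 11.2, it is 84.6%. This alpha inconsistency is a separate matter.
- A1c, Δ = 0.5, SD = 1.0, alpha 0.017: 85.4% (stated 84%).

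**Effect of the rule and of the fix on PAM-13 at alpha 0.025**

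Assumptions, none of them in the documents:
- A share p of patients, 2% to 5%, becomes pregnant (0.02 × 240 ≈ 5 to 0.05 × 240 = 12 women).
- These come on top of the 20% attrition and are spread evenly over the two sites.
- Timing is uniform over 12 months, so half begin after month 6 and keep an observed 6-month outcome under the fix.

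Whole record dropped: n = 120 × (1 − p) × 0.80.
Earlier visits kept: n = 120 × (1 − p/2) × 0.80.

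| p | n, dropped | Power | n, kept | Power | Recovered |
|---|---|---|---|---|---|
| 2% | 94.1 | 89.4% | 95.0 | 89.7% | 0.3 points |
| 5% | 91.2 | 88.3% | 93.6 | 89.2% | 0.9 points |

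The full loss from 90.0% is 0.6 to 1.7 points. The fix recovers about half, because a pregnancy beginning before month 6 still leaves no usable 6-month value.

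**Possible shift in a site mean**

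If a share s of one site's patients is removed and they differ from those retained by D standard deviations, that site's mean moves by s × D. With s = 2% to 5%, D = 0.25 to 1 and no removals at the other site, the shift is 0.02 × 0.25 = 0.005 SD to 0.05 × 1 = 0.05 SD. The hypothesized differences run from 0.5/1.0 = 0.50 SD to 2.2/3.8 = 0.58 SD.

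**The case against.** The strongest reply is that 3.3 never says visits before the pregnancy are to be dropped, and that section 13, which governs withdrawal, is silent. A reader might infer that the protocol expressly orders earlier visits discarded. It does not: whole-record removal follows from the unrestricted wording of 3.3 together with 3.2. It is still the natural reading, and nothing contradicts it, so an analyst following the text would drop the record.

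A reader might also infer a contradiction with the intention-to-treat analysis in 13.3. The documents do not support that. The term appears once, paired with per-protocol, as an example of a sensitivity analysis in a non-randomized study, and is not defined. An undefined set cannot be shown to conflict with 3.3; it can only be asked to say whether these women belong to it.

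The size can fairly be challenged too. The pregnancy rate is assumed. If pregnancy withdrawals already sit within the 20% attrition, the planned 96 per site does not change. Nothing shows that pregnancy rates differ by site: 11.1 expects similar populations and puts sex and age in the propensity score. That addresses differences in age mix but not selection after entry.

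**Conclusion.** The point holds as a cheap improvement to a stated rule. As written, 3.3 read with 3.2 removes data that its own rationale does not reach, including completed primary outcomes for pregnancies beginning after month 6, and it conditions the analysis set on a post-baseline event detected partly through A1c.

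The numerical effect is small. Correcting the rule is worth about 0.3–0.9 points of PAM-13 power at alpha 0.025, given a 2–5% pregnancy rate on top of attrition and uniform timing. A shift in a site mean would be at most 0.05 SD under the assumptions shown. A reader might infer material bias or a serious loss of power, or that the fix restores every lost endpoint; the figures support none of these. The case rests on keeping valid data and on a clean definition of the analysis set.

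**What to change.** In 3.3, replace the closing clause on data with: *data from visits completed before the estimated start of pregnancy (or, if unknown, up to the last visit at which she reported not being pregnant) are retained in the analysis; later data are set to missing and handled by the mixed model for A1c, BMI and PHQ-9 and by multiple imputation for DKQ and PAM-13 change.* The separate treatment is needed because the power for DKQ and PAM-13 in 11.2 rests on regression of change scores, where a record without month 6 contributes nothing unless imputed.

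Add a matching sentence to 13.3 and align 3.2, so that the exclusion ends participation without removing earlier data. State in 13.3 that the intention-to-treat set includes these women. Report their number by site.

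The cost is a few sentences, with no new data or visits. The downside is that a timing rule is needed, since pregnancy status is asked at visits three to six months apart, and a visit in very early, unrecognized pregnancy may be kept. A sensitivity analysis excluding these women checks that.

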Eligibility Screening: potential participants who agree to being screened for eligibility will be contacted by a member of the research team and asked the eligibility screening questions, including requesting information about a potential social support partner. The patient participant will be offered the opportunity to contact their potential social support partner to inform him or her that a research team member will be in contact to conduct an eligibility screening. When the patient partner gives permission to contact the potential social support partner, a member of the research team will contact the potential social support partner and conduct the eligibility screening. If both the patient participant and his or her social support partner are deemed eligible, baseline data collection appointments will be scheduled with both participants. The information collected during the eligibility screening will be hand-written on an Eligibility Screening form and given to the Patient Engagement Coordinator, who will enter it into REDCap in the Eligibility Screening project. The Patient Engagement Coordinator will then create a record for the participant in the PCORI Diabetes Project in REDCap and assign a participant ID (PID) to the participant. The Patient Engagement Coordinator will keep a master list of the participants' names and PIDs both electronically and in hard copy. The electronic copy will be saved on her password-protected laptop, which is stored in a locked cabinet at One Hope when not in use. The hard copy will also be stored in a locked cabinet at One Hope.

Data Collection: at the baseline data collection appointment, the PDCS will collect and enter contact and demographic information into separate data collection instruments in the PCORI Diabetes Project in REDCap. At the baseline and all three follow-up appointments, the PDCSs will also administer the survey instrument to the participants, responses to which will be entered into a third data collection instrument in the same project. The PDCSs will also collect BMI measurements (weight and height) and draw blood for A1c testing at the baseline and all follow-up appointments and will collect a hair sample at the baseline and six-month follow-up appointment. The BMI measurements will be entered into a fourth data collection instrument in the PCORI Diabetes Project by the PDCS during

PROTOCOL TITLE: Comparing Program Options for Latinos with Diabetes

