We do not foresee any major risks, hazards or side effects to the subjects related to participation in the research. Risk of a breach of privacy is low because of procedural safeguards in place and because RedCAP is a secure data capture system and because access to identifying information will be limited. Some individuals feel anxious when they answer questions about themselves or their experiences and perspectives. To minimize the risk of this, before gaining informed consent of individuals, investigators will clearly explain the research, the risks to participants, and the procedures for safeguarding their privacy. Participants will be informed that they can refuse to answer any questions and stop the survey, interview, data collection, or participation in a focus group at any time. The investigators will have training and will understand the importance of these issues and their responsibility for maintaining high ethical standards and they will have current human subjects research training certification. In relation to A1c, participating in our study will not impact A1c levels, but because we will be gathering information about patient A1c, we have developed a response protocol if we detect elevated A1c levels: For A1c (>10), we will notify the participant's PCP. For A1c (>10), we will notify the participant's PCP. If we see a lab value that could indicate an emergency (Glucose > 400 mg/dl, < 60 mg/dl), we will contact the participant to make sure they are aware of their A1c status and that

PROTOCOL TITLE: Comparing Program Options for Latinos with Diabetes

they are receiving appropriate care. For women with an elevated A1c, when we contact them to tell them about their elevated test results we will inquire again whether or not they are or think they might be pregnant. If so, Co-Investigator [name] will provide them with a referral to UNM's High Risk Obstetrics Clinic and they will be excluded from the study.

2. *All drugs and devices used in the research and the purpose of their use, and their regulatory approval status.*
N/A
3. *The source records that will be used to collect data about subjects. (Attach all surveys, scripts, and data collection forms.)*

Attached please find:

1. One Hope Waiting Room Flyer
2. One Hope Patient Recruitment Script (Revised)
3. CDE-UNMH Patient Recruitment/Consent Script (Revised)
4. CDE-UNMH Patient Recruitment Letter
5. Social Support Recruitment Script (Revised)
6. Staff & Provider Interview Recruitment Script

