The PDCSs will gather data from the participants for the contact information, the participant data sheet and the survey orally and enter the answers directly into password-protected tablet. If the tablet is able to be connected to wireless internet at the location, then the data will be entered directly into the secure UNM REDCap data storage system using a database created specifically for this project. BMI data will also be entered into the tablet. If there is no wireless internet connection at the data collection point, the PDCS will upload the data when there is. If entering the data onto the tablet is not possible for some reason, the PDCS will use paper copies of the instruments and later the responses will be double data entered by the Project Coordinator and the Co-PI into REDCap, where the Data Manager will conduct a double data entry analysis to ensure quality.

Blood will be gathered for A1c testing and labeled with the PID. Blood samples will be transported in a padded biohazard transport bag. They will be stored at room temperature at One Hope Clinic in a locked office. Three times a week, the Patient Engagement Coordinator will deliver the blood samples to the UNM CTSC lab for testing. Following testing, the lab will destroy the blood samples using standard laboratory protocol. Results of the blood testing will be sent to both the PI and the Data Manager in hard copy (the results sheet will not include any identifying information, only the PID). The PI will ensure that the Data Manager has entered the results into the database, and then the hard copies of results will be stored in a locked filing cabinet in the Data Manager's locked office for three years (for quality check purposes) when it will be destroyed.

The PDCS will use scissors to collect a pencil lead-width of hair from the crown of the head. One centimeter of hair closest to the scalp will be used to measure hair to determine the average cortisol level

PROTOCOL TITLE: Comparing Program Options for Latinos with Diabetes

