25.0 Provisions to Protect the Privacy Interests of Subjects

25.1 Describe the steps that will be taken to protect subjects' privacy interests. "Privacy interest" refers to a person's desire to place limits on whom they interact or whom they provide personal information.

Privacy and Confidentiality: Guidelines for the protection of participant privacy and confidentiality will be followed in all cases. All members of the research team will maintain current Human Subjects training. They will understand the importance of privacy issues and their responsibility to maintain the highest research ethical standards in all respects. Surveys, blood-draws and other clinical data gathering, interviews and focus groups will be conducted at a location to provide privacy. Prior to beginning each focus group, the facilitator will instruct participants regarding privacy measures. All participants will be asked to sign a receipt for a merchandise card incentive which will be used for project accounting purposes only and will not be linked with or associated with research data. Potential participants' contact and eligibility screening information will be kept in separate projects on REDCap. Enrolled participants' contact information, demographic information, survey responses, and biological measures will be entered and stored in separate data collection instruments within a third project in REDCap. The PID assigned to eligible

PROTOCOL TITLE: Comparing Program Options for Latinos with Diabetes

participants will be retroactively assigned to these participants' records in the Pre-Screening and Eligibility Screening projects, making this the only link across the three projects. The Study ID generated by REDCap will be the only link across the data collection instruments within the PCORI Diabetes Project. User rights to the three projects will be limited such that personally identifying information is only accessible to a few members of the research team. All biological samples will be uniquely labeled with the Participant ID.

We need to be able to maintain a link between the participant and the data to be able to notify participants if their A1c level is dangerously high or to be able to notify the participant's PCP if their A1c is above 10, to schedule follow-up appointments at 3, 6, and 12 months, and to be able to invite the participant to the end-of-study presentation of project results.

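### The emergency participant-contact rule is triggered by glucose values, but the only blood analyte the study plans to obtain is A1c

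*Combined protocol and SAP*

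**What the plan says.** The rule appears three times with identical cut-offs: in section 3.3 ("If we see a lab value that could indicate an emergency (Glucose > 400 mg/dl, < 60 mg/dl), we will contact the participant"), in the A1c paragraph of section 9.2 ("could indicate an emergency (Glucose > 400 mg/dl, < 60 mg/dl), we will contact the participant") and in section 9.3, item 1. Section 9.3 introduces it with the words "we have developed a response protocol if we detect elevated A1c levels". The stated aim of the contact, in section 3.3, is "to make sure they are aware of their A1c status and that they are receiving appropriate care".

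On the blood itself, section 9.2 says that the data collectors will "draw blood for A1c testing at the baseline and all follow-up appointments". It sends the samples to the CTSC laboratory for its hemoglobin A1c "procedure using the DCA Vantage 2000 analyzer".

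Two further strands sit beside the glucose rule:

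- **Provider notice.** Sections 3.3, 9.2, 9.3 and 25.1 have the study inform the participant's primary care provider when A1c is above 10.
- **A1c-based participant contact.** Section 25.1 keeps the identity link in order to "notify participants if their A1c level is dangerously high". Section 11.5 (item 2), the resources section numbered 21.0 and section 28.1 (item 4) describe similar contact on a high, concerning or elevated A1c.

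**The concern.** A safety rule works only if the study produces the value that triggers it. Here the trigger is glucose, while every description of the blood work concerns A1c. The rule is also inconsistent in itself: section 9.3 presents it as a response to raised A1c, its trigger is a high or low glucose, and its action is a conversation about A1c.

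What is at stake is consistent handling of an urgent laboratory result. Staff have one numeric participant-contact trigger that their results cannot meet, and several A1c wordings with no number. Two staff members could treat the same A1c result differently and both be following the protocol. Section 12.0, on monitoring data for participant safety, is marked not applicable, so nothing there settles the matter.

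**Working it through.** No formula applies. The check was to find every use of glucose in the document and every description of the blood draw, assay, results and data list, and to set them side by side.

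**Step 1: where glucose appears.**

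| Place | Role of glucose |
|---|---|
| 3.3 | Emergency trigger, > 400 or < 60 mg/dl |
| 9.2, A1c paragraph | Same trigger |
| 9.3, item 1 | Same trigger |
| 2.1 | Background: patients' self-monitoring |
| 9.2, hair cortisol paragraph | Background: physiology |

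That is three statements of the trigger. The remaining uses are background.

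**Step 2: what the study obtains from blood.**

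| Place | Analyte named |
|---|---|
| 9.2 and 25.3, purpose of the draw | A1c |
| 9.2, laboratory procedure | A1c; the reference cited for the analyzer is an A1c validation study |
| 11.5, item 1, test on delivered specimens | A1c |
| 11.5, item 1, value taken from CDE-UNMH program files | Baseline A1c |
| 11.5, item 6, purpose of transported blood | A1c |
| 9.2 and 25.3, six REDCap instruments | A1c is the only blood result (the other laboratory result is hair cortisol) |
| 9.4, list of data collected | A1c, BMI and hair samples; no glucose |

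No place provides for a glucose value.

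**Step 3: which response rules can operate on planned data.**

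| Rule | Analyte | Numeric threshold | Can be met from planned data |
|---|---|---|---|
| Emergency participant contact (3.3, 9.2, 9.3) | Glucose | Yes | No |
| Provider notice (3.3, 9.2, 9.3, 25.1) | A1c | Yes (> 10) | Yes |
| Participant contact (11.5, 21.0, 25.1, 28.1) | A1c | None | Only by unstated judgement |

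The only numeric participant-contact trigger rests on an analyte that is not planned. The participant contact that rests on the planned analyte has no number. Section 25.1 names the participant notice separately from the provider notice above 10, so that figure cannot simply be carried over to the participant.

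**The case against.** The strongest reply is that participants would be contacted anyway. Sections 11.5, 21.0, 25.1 and 28.1 all describe contact on A1c. Sections 3.3, 9.2 and 9.3 speak of telling women about an elevated A1c, and section 15.1 says patients receive their A1c results. This stands, and it limits the point. A reader might infer that the provider notice is the only safety action left, or that no participant could ever be contacted about a worrying result. The documents do not support either reading. What is missing is a usable threshold for participant contact, not the intention to make it.

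Three further inferences should also be resisted:

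- **Access to care.** A reader might argue that relying on the provider route is unsafe because these patients struggle to reach care. Section 2.3 reports limited resources and program shortcomings, but it does not say that enrolled patients lack a provider. Section 3.2 requires that a provider identified each patient.
- **Batched delivery.** Section 11.5 says: "Three times a week, the Patient Engagement Coordinator will deliver the blood samples to the UNM CTSC lab for testing". It is tempting to call this too slow for an emergency value. With no glucose assay planned there is no glucose alert to delay, and no section sets a turnaround for A1c that this schedule would break.
- **A count of draws.** Four draws for each of 240 patients gives 240 × 4 = 960. But section 11.5 takes the CDE-UNMH baseline from program files, which gives 120 × 4 + 120 × 3 = 840, while section 9.2 has every baseline drawn. Either figure only restates that glucose is not planned.

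It is also fair to say that the laboratory's own procedure is not reproduced, and that a glucose value could reach the team from outside the study. Nothing in the plan provides for that.

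Finally, the study is data collection only and is declared minimal risk. That bears on how serious the point is, not on whether the rule can work.

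**Conclusion.** The point holds, limited to the glucose-triggered contact. Three sections state an emergency rule on glucose, and no section provides for a glucose value, so the rule cannot be met from planned study data. This is a contradiction within the plan and not merely a missing detail. Alongside it, four sections describe participant contact on A1c without a threshold. The provider notice at A1c above 10 is unaffected and can operate.

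The conclusion assumes that the blood work consists of what the document describes and that the CTSC laboratory does not also return glucose. If it does, the plan should say so. The point concerns safety procedure only. No endpoint, sample size, alpha, power figure or analysis changes. It should be corrected because the team chose to define an emergency contact and the definition does not work as written.

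**What to change.** Reconcile the trigger in sections 3.3, 9.2 and 9.3 with the laboratory and data descriptions in 9.2, 9.4, 11.5 and 25.3, and with the contact wording in 11.5 (item 2), 21.0, 25.1 and 28.1 (item 4). The result should be one participant-contact rule, set by the responsible clinician and used throughout, on an analyte the study actually obtains. If glucose is in fact measured, state where, by what assay, and how the result is recorded and reported. If it is not, the clinician should restate the trigger on the measured analyte and decide what becomes of both the high and the low limb of the present rule. Which analyte or threshold is right is a clinical decision, and none is proposed here.

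The cost is protocol wording and clinician sign-off. If the rule is restated on A1c, no procedure is added.
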